MSI-R (AFC, PSC)	Marital Satisfaction Inventory-Revised (Affective Communication, Problem-Solving Communication Subscales)
EDQOL	Eating Disorders Quality of Life
CSQ	Client Satisfaction Questionnaire

PROTOCOL SYNOPSIS

Study Title	Targeting Relationship Domains in Community-Based Treatment of Binge-Eating Disorder
Funder	NIMH
Study Rationale	Clinicians' options for BED treatment are inadequate. Treatments for BED have demonstrated efficacy in controlled settings with specialist therapists and expert supervision, but much less is known about the effectiveness of BED interventions and whether the transition of evidence-based treatments to the community results in poorer outcomes. UNITE activates a key resource by incorporating an important part of the patient's social environment (the partner) into treatment. The investigators hypothesize that UNITE will show preliminary evidence of being superior to CBT-E in achieving binge abstinence via engaging ED-related relationship targets, including improved (a) communication around the disorder, (b) disorder-specific interpersonal problem-solving/ behavioral change skills, and (c) partner-assisted emotion regulation. The investigators will assess targeted relationship domains with observational and speech prosody measures during clinic interactions and self-reports reflecting experiences outside of the clinic. Because the couple is learning how to work together to address BED, the investigators hypothesize that maintenance of gains will show evidence consistent with superiority in UNITE.
Study Objective(s)	Primary 
• To compare the effectiveness of UNITE versus CBT-E in achieving abstinence from binge-eating. Secondary 
• To compare the effectiveness of UNITE versus individual CBT-E in decreasing ED-related psychopathology, depression, and anxiety.• To compare target relationship domains in patients and partners.• To compare treatment satisfaction and ED-related quality of life in UNITE versus CBT-E
Study Design	38 couples will be enrolled over 18 months (to aim for 34 couples who complete the intervention). Each couple will be randomly assigned to UNITE or CBT-E and will undergo 16 weeks of study treatment. Preliminary efficacy (e.g., changes in binge-eating frequency, depression, anxiety, and relationship functioning) of UNITE will be assessed in comparison to the control group (CBT-E). Treatment gains will be assessed including observational and self-report measures.
Subject Population key criteria for Inclusion and Exclusion:	Inclusion Criteria 
1. Subjects age 18 – 992. Current DSM-5 criteria for BED (one partner per couple)3. English speaking and able to read4. In a committed relationship for at least 6 months (regardless of sexual orientation)

5. Live with partner (or interact with each other daily)
6. Partner willingness to participate in treatment
7. Able to travel to Chapel Hill, NC weekly for treatment (N.B. Changed in 3/20 to "in North Carolina" due to pandemic)

Exclusion Criteria

1. Alcohol or drug dependence in the past year
2. Current anorexia nervosa; current bulimia nervosa
3. Current significant suicidal ideation with active suicidal intent
4. Severe depression that would seriously interfere with functional capacity
5. Developmental disability that would impair the ability to benefit from the intervention
6. Any psychosis, schizophrenia, or bipolar I disorder, unless stably remitted on maintenance therapy for at least 1 year
7. Moderate to high reported levels of physical violence from either partner
8. Unwillingness to forgo non-protocol concurrent couple therapy
9. Previously participated in the UNITE pilot trial

Number of Subjects	76 (38 couples)
Study Duration	Each subject's participation will last approximately 20-30 hours over 10 months. The entire study is expected to last two years.
Study Phases Screening Study Treatment Follow-Up	
(1) Screening: After consenting to participate and completing an initial phone screening, potential participants will be asked to complete a pre-treatment assessment consisting of electronic questionnaires and an in-person interview in order to determine eligibility for the study. These assessments will ask questions about a range of relationship concerns and interaction patterns as well as eating behaviors. The participant with BED in each couple must provide written certification from their PCP that their health status is suitable for this study. After determining eligibility, patients will be randomized to either UNITE or CBT-E and receive 16 approximately one-hour sessions of the respective treatment.
 
(2) Intervention:
 
 • UNITE is a manualized CBCT intervention that engages the couple to address the core psychopathology of BED and targets improved: 
 ○ Communication around the ED ○ Interpersonal problem-solving and behavioral change skills ○ Partner-assisted emotion regulation • CBT-E is a manualized CBT intervention for ED with four stages of treatment: 
 ○ Psychoeducation and symptom self-monitoring ○ Review progress and formulate plans for future

- Reducing ED behaviors and improve mood tolerance
- Maintaining progress and minimizing relapse risk

(3) Follow-Up: Participants will complete follow-up assessments:

- at the end of treatment
- 3 months after the completion of treatment
- 6 months after the completion of treatment

Efficacy Evaluations	Recruitment, enrollment, retention, and follow-up targets met.
-----------------------------	--

Safety Evaluations	The clinical status of all participants will be monitored closely by the study team. If information about a participant is generated that warrants concern (such as participant suicidality or danger to self or others), the research team will follow an established safety protocol to assess for immediate participant danger or safety. Participants will be provided with appropriate crisis resources if needed at the time of assessment. If concerns are identified that require additional support (for either the patient or the partner), the research team will work to find the participant an appropriate professional referral from an internal referral list of therapists, psychiatrists, nutritionists, and other mental health professionals.
---------------------------	---

Outcomes	
Primary outcome: Eating Disorder Examination-Questionnaire (EDE-Q) abstinence from binge eating (Fairburn & Beglin, 1994).
 
Secondary outcomes will include ED symptoms, depression and anxiety, couple-based measures, treatment satisfaction, and quality of life. ED symptoms will be measured with the Eating Disorder Examination-Questionnaire (EDE-Q; 28 items) binge frequency and global score (Fairburn & Beglin, 1994), the Binge Eating Scale (BES; 16 items) which measures binge eating severity (Gormally et al., 1982), and the Yale-Brown Obsessive Compulsive Scale Modified for Binge Eating (Y-BOCS-BE; 10 items) which measures the obsessiveness of binge-eating thoughts and compulsiveness of binge-eating behaviors (Deal et al., 2015). Beck Depression Inventory-II (BDI-II; 21 items) and Beck Anxiety Inventory (BAI; 21 items) will measure severity of current depressive and anxiety symptoms, respectively (Beck et al., 1988; Beck et al., 1996). Difficulties in Emotion Regulation Scale (DERS; 36-item) and the partner version (DERS-Partner; 8 items) will measure emotion regulation in oneself and one's partner, respectively (Gratz & Roemer, 2004). Dyadic Adjustment Scale (DAS; 32 items) and DAS-4 (4 items) will measure relationship satisfaction. Communication Patterns Questionnaire-Short Form (CPQ-SF; 12 items (Christensen & Heavey, 1990) modified for BED has two scores that will be calculated to assess how the couple communicates about the ED. These are a total score made up of the Self Demand/Partner Withdraw and Partner Demand/Self Withdraw subscales (6 items) and the Constructive Communication subscale (3 items). Marital Satisfaction Inventory (MSI-R; 32 items) affective communication (AFC) and problem-solving/communication (PSC) subscales will be used (Snyder, 1997). Treatment satisfaction will be measured with the Client Satisfaction Questionnaire (CSQ; 18 items). (Nguyen et al., 1983). Eating

-----------------	---

Disorders Quality of Life (EDQOL; 26 items) will measure the extent to which the ED affects quality of life (Engel, 2003). ED-related measures will be given to patients only and all other measures will be given to patients and partners.	
Statistical and Analytic Plan	Intent-to-treat or modified intent-to-treat, if appropriate, will comprise the primary approach. Differential treatment effects will be analyzed with multilevel mixed-effects models with fixed effects and interactions for Time, Treatment, and (where appropriate) Participant Status (i.e., patients/partners), and with random effects to address clustering.
Data and Safety Monitoring Plan	The DSMG will be responsible for data quality management and ongoing assessment of participant safety.

1 BACKGROUND AND RATIONALE

1.1 Introduction

Clinicians' options for EDs (ED) treatment are inadequate. EDs challenge caregivers and strain relationships (Van den Broucke & Vandereycken, 1988; Van den Broucke et al., 1994, 1995, 1995; Whisman et al., 2012). Partners are typically excluded from treatment. Family involvement improves outcomes in youth (Ie Grange et al., 2010) and in adults with anorexia nervosa (AN) (Baucom et al., 2017). Engaging partners improves weight gain in AN, reduces high drop out in AN (Baucom et al., 2017) and binge-eating disorder (BED) (Runfola et al., 2018), and may lead to greater binge-eating abstinence (Runfola et al., 2018). As BED awareness and treatment demand increases post DSM-5, the field will benefit from scalable interventions.

- Name and Description of Intervention: The experimental treatment, UNITE, is a manualized cognitive-behavioral couple therapy (CBCT) intervention that engages the couple to address the core psychopathology of BED. It includes three stages: early treatment (psychoeducation and understanding the couple's experience of BED within the relationship); mid-treatment (effective communication, interpersonal problem-solving, and emotion regulation skills), and late treatment (relapse prevention). Additional relevant topics may be covered including body image, weight stigma, weight and health concerns, and intimacy and sexuality issues.

The active comparator, CBT-E, is a trans-diagnostic cognitive behavioral individual therapy treatment for eating disorders. It has been shown to be effective in numerous controlled and open trials. It includes four stages: an introductory stage (psychoeducation, normalization of eating patterns, and symptom self-monitoring); a second, brief stage (review progress and formulate plans for the subsequent treatment phase); a third stage (elimination of dieting, reducing shape checking and avoidance behaviors, educating about mood tolerance, and targeting over-evaluation of shape and weight); and the fourth stage (maintaining progress and minimizing relapse risk).

1.2 Non-Clinical and Clinical Study Findings

- Potential Benefits: This is a treatment research study in which all patients enrolled will receive an intervention for BED (regardless of the treatment group to which they are randomized). Although the investigators cannot guarantee that patients will derive any benefit from the study, the likelihood is fairly high that patients will benefit to some degree from the study. Results of this study could enhance treatment of BED. If implementation of the couple program is feasible and efficacious, couple treatment may show promise in increasing treatment response rates and maintaining engagement after formal treatment. Training for a couple-based approach to the treatment of BED could also then be implemented in other non-specialty settings, thus increasing patient access to care.

- Risk /Benefit Assessment: Participants may find participation in clinical interviews or the videotaped assessments to be unpleasant or distressing. Similarly, any psychotherapeutic intervention may be associated with discomfort consequent to discussion of painful symptoms or problems. Some participants may find the couple format uncomfortable. A number of steps will be taken to protect participants against possible risks. All study personnel will be trained to be sensitive to participants' concerns and will make it clear to participants that participation in the study is voluntary and that they may withdraw from the study at any time. Participants will be directed to alert study personnel if there is a change in their psychological condition. Strict confidentiality will be maintained with any use of participants' medical records or claim files in accordance with federal, state, and local policies. Research data will be maintained in separate charts and identified by participant number only. Clinical supervision of UNITE and CBT-E study treatment will each be conducted by a licensed psychologist with a one-hour weekly group supervision meeting. Thus, through initial training and weekly supervision, the investigators will provide supervision commensurate with the practice of the community clinic.

1.3 Relevant Literature and Data

Treatments for BED and bulimia nervosa (BN) have demonstrated **efficacy** in controlled settings with specialist therapists and expert supervision (Brownley et al., 2016; Shapiro et al., 2007). Much less is known about the **effectiveness** of BED/BN interventions and whether the transition of evidence-based treatments to the community results in poorer outcomes. One strategy to bolster the effectiveness of BED/BN treatment in real world conditions is to **activate resources in the patient's environment** (Grawe, 2007). Including partners in treatment is one such resource and is defensible, as 22-46% of BN patients (Carter et al., 2003; Ghaderi, 2006; Poulsen et al., 2014) and 60-77% of BED patients (Safer & Jo, 2010; Schlup et al., 2010) are married or co-habiting, comparable to healthy controls (Maxwell et al., 2011). Partners are eager to help yet unsure what to do (Kirby et al., 2015).

Relationships can also be a source of stress, as BED/BN patients report higher levels of relationship distress, negative interactions, and poorer communication than those with other psychiatric disorders (Van den Broucke & Vandereycken, 1988; Van den Broucke et al., 1994, 1995, 1995; Whisman et al., 2012). The transdiagnostic theory of EDs highlights adverse interpersonal environments as illness-maintaining factors (Fairburn et al., 2003), and interpersonal theory targets interpersonal stressors as binge/purge triggers via their contribution to negative affect (Arcelus et al., 2013). Patients also cite interpersonal stressors as common binge/purge triggers, as confirmed by ecological momentary sampling (Goldschmidt et al., 2014; Hilbert et al., 2011). **Including a partner in treatment facilitates transformation of the relationship from a stressor into an agent of positive change.**

The investigators have incorporated partners in the treatment of adult psychiatric disorders, using adaptations of cognitive-behavioral couple therapy (CBCT) (Abramowitz et al., 2013; Baucom et al., 2017; Baucom et al., 1998; Sher et al., 1990). The investigators demonstrated initial efficacy of our couple-based ED treatments in a university hospital specialist setting (Baucom et al., 2017; Bulik et al., 2011; Kirby et al., 2015). The investigators developed a CBCT intervention for BED/BN (UNiting couples In the Treatment of Eating disorders [UNITE]). Here the investigators test the preliminary comparative effectiveness of UNITE versus individual CBT-enhanced (CBT-E) (a transdiagnostic treatment for EDs) in a small randomized controlled trial (RCT) of 28 couples in a community clinic. Because UNITE activates a key resource by incorporating an important part of the patient's social environment (the partner) into treatment, the investigators hypothesize that UNITE will show preliminary evidence of being superior to CBT-E in achieving binge/purge abstinence via engaging ED-related relationship targets, including improved (a) communication around the disorder, (b) disorder-specific interpersonal problem-solving/ behavioral change skills, and (c) partner-assisted emotion regulation. Targeted relationship domains will be assessed with observational and speech prosody measures during clinic interactions and self-reports reflecting experiences outside of the clinic. Because the

couple is learning how to work together to address BED/BN the maintenance of gains are hypothesized to show evidence consistent with superiority in UNITE.

2 STUDY OBJECTIVE

2.1 Primary Objective: The purpose of this study is to test the feasibility, acceptability, and preliminary effectiveness of a novel couple-based intervention for BED (UNITE) relative to an established evidence-based individual treatment (CBT-E) in a community clinic setting.

3 INVESTIGATIONAL PLAN

3.1 Study Design

Type of design: Randomized controlled trial

Brief overview of the study phases: see Protocol Synopsis “Study Phases”

3.2 Study Duration, Enrollment and Number of Subjects

38 couples will be enrolled over 18 months (to aim for 34 couples who complete the intervention). Each couple will be randomized to either UNITE or CBT-E and will undergo 16 weeks of treatment, followed by follow-up assessments at the end of treatment and 3- and 6-months after the end of treatment.

3.3 Study Population: see Protocol Synopsis “Subject Population”

4 STUDY PROCEDURES

4.1 Screening/Baseline Visit procedures

Pre-Treatment

1. Patient and partner come in for pre-treatment visit, which includes the following:

- Consent with both patient and partner
- Videotaped couple interaction
- Interviews
- Self-report Questionnaires

2. Eligibility is determined

3. Couple is randomized to UNITE or CBT-E condition

4. Therapist is assigned and notified

- Baseline (Pre-Treatment)

- Consent
- Background information
 - *Background Information* (1 min). This questionnaire asks questions about age, sex, race/ethnicity, socioeconomic status, and relationship history.
- Couple Interaction
 - Couple is recorded having two 10-minute conversations:
 - For the first conversation (“sharing thoughts and feelings”) the couple is given the prompt: Please select an issue in your relationship related to [patient’s] eating disorder, sharing your thoughts and feelings with each other about this issue. Don’t attempt to resolve it, just let each other know what you think and feel. Try to select something that you view as being of a moderate level of concern or intensity.
 - For the second conversation (“problem-solving”), the couple is given the prompt: I will again ask you to select an issue in your relationship related to [patient’s]

eating disorder, but this time you will discuss ways you could resolve or improve this issue. Try to select something that you view as being of a moderate level of concern or intensity. That is, don't select something trivial, but also don't select the most difficult concern that you have."

- For each conversation, the interviewer may assist the couple in identifying a topic for conversation. Then, the interviewer leaves the room during the 10-minute recorded conversation.
- Vitals (Patient, Partner)
 - Self-reported height, weight, BMI
- Questionnaire (Patient, Partner)
 - ED100K, EDE-Q, BES, BE frequency, BDI-II, BAI, DERS, DERS-Partner, DAS, CPQ-SF, R-BISF, CTS-2, MSI-R, EDQOL
- Interview (Patient, Partner)
 - Videotaped couple interaction
 - MINI, YBOCS-BE

4.2 Intervention/Treatment procedures (by visits)

Both UNITE and CBT-E have 16 treatment sessions

Weekly questionnaires to be completed by the participants in treatment

Weekly Questionnaires consist of binge eating frequency assessment, DAS-4

For UNITE, Patient and Partner fill out questionnaires. For CBT-E, only Patient.

Mid-treatment assessment after session 8 is completed

End-treatment assessment after session 16 is completed

Mid-Treatment (after Session 8)

- Vitals (Patient, Partner)
 - Self-reported height, weight, BMI
- Questionnaire (Patient, Partner)
 - EDE-Q, BES, BE frequency, BDI-II, BAI, DERS, DERS-Partner, DAS, CPQ-SF, R-BISF, MSI-R, EDQOL
- Check BDI for suicidality
- YBOCS-BE Interview (Patient)

Post-Treatment (after Session 16)

- **Couple Interaction**
- Vitals (Patient, Partner)
 - Self-reported height, weight, BMI
- Questionnaire (Patient, Partner)
 - CSQ, EDE-Q, BES, BE frequency, BDI-II, BAI, DERS, DERS-Partner, DAS, CPQ-SF, R-BISF, MSI-R, EDQOL
- YBOCS-BE Interview (Patient)
- Therapist Feedback (Therapist)

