4.3 Follow-up procedures (by visits)

*N.B.: virtual after 3/20.

- 3-Month Follow-Up
 - Vitals (Patient, Partner)

- Height, weight, BMI, blood pressure, heart rate
- Questionnaire (Patient, Partner)
 - EDE-Q, BES, BE frequency, BDI-II, BAI, DERS, DERS-Partner, DAS, CPQ-SF, R-BISF, MSI-R, EDQOL
- \$50 visa card upon completion
- 6-Month Follow-Up
 - Vitals (Patient, Partner)
 - Self-reported height, weight, BM
 - Questionnaire (Patient, Partner)
 - EDE-Q, BES, BE frequency, BDI-II, BAI, DERS, DERS-Partner, DAS, CPQ-SF, R-BISF, MSI-R, EDQOL
 - YBOCS-BE Interview (Patient)
 - \$50 visa card upon completion

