5 STUDY EVALUATIONS AND MEASUREMENTS

5.1 Efficacy Evaluation

Preliminary efficacy (e.g. changes in binge-eating frequency, depression, anxiety, and relationship functioning) of UNITE will be assessed in comparison to the control group (CBT-E). Treatment gains will be assessed including observational and self-report measures. The primary outcome is abstinence from binge eating over the past 28 days measured with the EDE-Q. Secondary outcomes include EDE-Q binge frequency and global psychopathology, BES, Y-BOCS-BE, BDI-II, BAI, DERS, DERS-Partner, DAS, DAS-4, CPQ-SF, MSI-R (AFC and PSC), CSQ, and EDQOL.

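### Does collecting the weekly DAS-4 from partners in UNITE but not in CBT-E leave a secondary outcome without a workable analysis?

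*Combined protocol and SAP*

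**What the plan says.** The Outcomes entry of the synopsis names the 32-item DAS "and DAS-4 (4 items) will measure relationship satisfaction". It ends by restricting eating-disorder measures to patients, while "all other measures will be given to patients and partners". Nothing there distinguishes the arms.

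Section 4.2 is the only place that schedules the DAS-4 by name. It introduces "Weekly questionnaires to be completed by the participants in treatment", gives their content ("Weekly Questionnaires consist of binge eating frequency assessment, DAS-4") and then states who completes them: "For UNITE, Patient and Partner fill out questionnaires. For CBT-E, only Patient".

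Section 5.1 lists the short form separately from the full scale: "Secondary outcomes include EDE-Q binge frequency and global psychopathology, BES, Y-BOCS-BE, BDI-II, BAI, DERS, DERS-Partner, DAS, DAS-4". Section 5.3 assigns models by class. Patient-only outcomes get Time, Treatment and their interaction. Outcomes measured in both members add Participant Status with all two- and three-way interactions. Treatment satisfaction is the only measure given its own rule. The synopsis describes the models as having "fixed effects and interactions for Time, Treatment, and (where appropriate) Participant Status".

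The full DAS is on the patient-and-partner questionnaire list at every assessment visit. At the 3- and 6-month visits, for example, the list in Section 4.3 reads "EDE-Q, BES, BE frequency, BDI-II, BAI, DERS, DERS-Partner, DAS, CPQ-SF, R-BISF, MSI-R, EDQOL". Table 3 codes the DAS row for both members and stars it, but the footnote to the star mentions only weekly binge and purge frequency.

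**The concern.** Read alone, the synopsis puts the DAS-4 among the outcomes measured in both members, and hence in the two-member model of Section 5.3. Under Section 4.2, CBT-E partners never complete it. The DAS-4 is then a two-member outcome in one arm and a patient-only outcome in the other, and fits neither model class cleanly.

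If the two-member model were fitted anyway, the terms describing how treatment affects partners would have no CBT-E data behind them. Software that drops aliased columns could report coefficients whose meaning depends on the coding. Comparing relationship domains in patients and partners is a stated secondary objective, so a reader could fear that part of it has been lost. Treatment satisfaction makes the omission more visible: Table 3 schedules it for both members, and Section 5.3 says outright that patients are compared. The DAS-4 has no such sentence.

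**Working it through.** The plan states no figure on this point, so there is none to reproduce. The check is whether the fixed effects of the two-member model can be estimated when one cell is empty.

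**Inputs.** Two arms and two member types (Section 5.3); no weekly forms from CBT-E partners (Section 4.2); 38 couples, with 34 intended to complete (Section 3.2); 1:1 allocation (Section 7); 16 sessions (Section 4.2). Two assumptions are added: an even split of couples, and one DAS-4 occasion per session.

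**Model.** Let T = 1 for UNITE and S = 1 for partner, with time w linear:

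mean = b0 + b1·T + b2·S + b3·T·S + w·(g0 + g1·T + g2·S + g3·T·S), giving 8 columns.

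**Intercepts, cell by cell** (slopes follow the same pattern with g in place of b):

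- CBT-E patient: b0, observed
- UNITE patient: b0 + b1, observed
- UNITE partner: b0 + b1 + b2 + b3, observed
- CBT-E partner: b0 + b2, not observed

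**What can be estimated.** The patient treatment effect is UNITE patient minus CBT-E patient = b1, and the patient Time x Treatment term is g1. Both come from observed cells. The partner-minus-patient difference within UNITE, b2 + b3, is also available, as is its slope counterpart g2 + g3.

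**What cannot.** Only the sum b2 + b3 is identified. So b3 (Treatment x Status), b1 + b3 (the partner treatment effect), b2 (Status within CBT-E) and g3 (the three-way term) are not.

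**Rank.** With k time parameters per cell, there are 4k columns and the rank is 3k.

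- Linear time, k = 2: 4 x 2 = 8 columns, rank 3 x 2 = 6.
- Sixteen categorical weeks, k = 16: 4 x 16 = 64 columns, rank 3 x 16 = 48.
- All four cells filled: 8 of 8 and 64 of 64.

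Building the matrices numerically gave the same ranks and the same estimable contrasts. The deficit comes from the empty cell alone. Adding couples or weeks does not alter it.

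**Alternatives already in the plan.** The patient-only model for the DAS-4 has 4 columns and rank 4. The two-member model for the 32-item DAS has all four cells filled: 8 of 8 with linear time, or 4 x 5 = 20 of 20 with its five assessments (pre, mid, post, 3 and 6 months) as categories.

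**Size of the empty cell.** 19 of 76 participants (25%) at 38 couples, or 17 of 68 (25%) at 34. This restates that one cell in four is empty. It is not a loss of information for the patient comparison.

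**The case for a change.** The strongest case for a change is that the DAS-4 is a separately named secondary outcome. The synopsis and Section 4.2 point to different models, and the choice ought to be on paper before the data are analysed. A sentence would do it and would need no new data. The plan also does not say which weekly occasions enter the analysis, and the promise in Section 12 of post-treatment and follow-up results on secondary outcomes has no matching DAS-4 collection.

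The wording gap and the algebra both stand. Less of the rest does:

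- The synopsis gives a one-sentence summary and does not say that every partner in both arms completes every form. Section 4.2 is the operative procedure. Its limit to those in treatment reads as a deliberate exception, because partners in individual CBT-E are not in treatment.
- The synopsis brings in Participant Status only where it fits, so nothing forces the three-way model onto the DAS-4.
- Section 5.3 names no outcome apart from treatment satisfaction, not even the primary one. Silence about the DAS-4 is the general style of the section.
- The timing is stated: weekly during treatment. Section 12 is a general publication plan and does not schedule the DAS-4 at follow-up.
- If an analyst did fit the two-member model, the empty cell would normally appear as a rank warning or dropped terms. The patient contrasts would still be estimable.

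**Conclusion.** No change to the plan is needed. This is a gap in wording on one secondary measure, and analysts would fill it sensibly. With no CBT-E partner scores, the only between-arm DAS-4 comparison the data can support is in patients over the weekly treatment occasions, and the patient-only model of Section 5.3 already provides it. Partner comparisons of relationship satisfaction come from the 32-item DAS, which measures the same construct, so the patient-and-partner objective survives.

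In the least favourable reading, the partner treatment effect, Treatment x Status, the Status effect within CBT-E and the three-way term, with the corresponding slope terms, cannot be estimated for the DAS-4 (rank 6 of 8 with linear time). No patient treatment contrast and no primary result changes. Writing the rule down would record a choice that the data collection has already made.

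The conclusion assumes that Section 4.2 was followed as written and that the full DAS was collected from both members in both arms as scheduled. The 25% figure also assumes an even split of couples; the rank result does not.
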